The third site is [REDACTED] located at [REDACTED] [REDACTED] [REDACTED].

This study is part of a larger project that focuses on investigating the implementation and effectiveness of Peer GLB. The present protocol focuses on the effectiveness trial using the RCT study, which is represented by Aims 1-3 outlined in the grant proposal for the current NIMH funded study (1R01MH104574-01: see grant attached). A different IRB protocol for the mixed methods implementation study (Aim 4) was previously submitted and approved: IRB-AAAN5207. We will be submitting as a protocol modification all Spanish translation of study materials (e.g., consent forms, capacity-to-consent, structured interviews) once the English versions have been approved.

2. Study Design and Statistical Procedures

We will use a randomized controlled trial design in order to test the effectiveness of Peer GLB vs. usual care (UC) in supportive housing agencies. Peer GLB lasts 12 months and consists of weekly core group sessions (3 months.), bimonthly (twice a month) transitional group sessions (3 months.), and monthly maintenance sessions (6 months). Peer specialists in the housing agencies will be trained and supervised by the study team and the supportive housing agencies to deliver Peer GLB. Repeated participant assessments conducted by trained study staff (e.g., research assistants) will occur at baseline and at 6, 12, and 18 months post-randomization.

Primary Aim:

1. Compare the effectiveness of Peer GLB vs. UC in achieving clinically significant weight loss (5% weight loss) among overweight/obese (BMI 25) clients in supportive housing agencies.

Primary Hypothesis: Peer GLB participants will have a higher proportion of persons achieving

clinically significant weight loss (5% weight loss) at 12 and 18 months than UC participants.

Secondary Aims:

2. Compare secondary outcomes: reductions in total weight, waist circumference, blood pressure, and improvements in physical activity, self-efficacy, recovery, and quality of life at 6, 12, and 18 months between Peer GLB and UC. Secondary Hypothesis: At 6, 12, and 18 months post- randomization, there will be significant reductions in average weight, waist circumference, blood pressure, and significant improvements in physical activity, self-efficacy, recovery, and healthrelated quality of life in Peer GLB compared to UC.

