Peer GLB, is based on an established group-based lifestyle intervention adapted from the original Diabetes Prevention Program (DPP) lifestyle program²⁶ by the DPP Lifestyle Resource Core at the

University of Pittsburgh's Diabetes Prevention Support Center (DPSC). Peer GLB is a goal-based behavioral intervention aimed to achieve loss and maintenance of 7% baseline body weight through modest dietary restrictions (e.g. reduce fat intake by <25%) and increase moderate physical activity (e.g., brisk walking) to 150 min/wk.²¹ GLB consists of weekly core group sessions (3 months), bi-monthly (twice a month) transitional group sessions (3 months), and monthly maintenance sessions (6 months.) delivered in community settings (i.e., supportive housing agencies.

Core features of Peer GLB include: integration of safe and appropriate nutritional education, physical activity and behavioral change, strong emphasis on the use of self-monitoring tools (e.g., food and physical activity logs) with regular feedback, and the incorporation of problem solving techniques to address barriers to healthy eating and physical activities. Examples of session topics and themes include: being a fat and calorie detective, healthy eating, move those muscles, problem-solving, four keys to healthy eating out, etc. The intervention includes a group facilitator curriculum manual and DVDs specifying session-by-session instructions, scripts, and group activities (e.g., portion size demonstrations, use of pedometers, problem solving steps) as well as participants' handouts for each session. Intervention materials are available in English and Spanish. Throughout the program, participants are given session handouts, commercially available fat and calorie-counting book, self- monitoring books to tracking food intake and physical activity, pedometers with instructions, program calendar, and a chart to self-monitor their weight twice a week over the course of the program. During session, participants are also shown the intervention DVD's to augment the educational content of the intervention. For English speaking participants, the Peer GLB groups will be delivered in English. For Spanish speaking participants, the Peer GLB groups will be delivered in Spanish.

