Lastly, participants assigned to the intervention will be asked to complete one semi-structured qualitative interview that focuses on the participants' experiences with the group facilitator and explores specifically how intervention services were delivered from the participants' perspective. This semi-structured qualitative interview will be conducted after the transition phase of an intervention group has been completed. Participants who attended at least two intervention sessions will be asked to complete the interview and a total of 55 participants are expected to participate. The interviews last approximately 90 minutes and will be conducted in person by Drs. [name] (PI) & [name] (PD) and/or a trained research assistant at the study site. Examples of questions include: Is there anything that makes the healthy lifestyle peer specialist/facilitator unique from other provider staff that you have worked with? What are some of the peer specialist's/facilitator's best qualities? What kinds of things did your peer specialist/facilitator do to model or show you how to engage in a healthy lifestyle?

Criteria for Early Discontinuation

Early discontinuation from the study will be ascertained by the group facilitator in consultation with the participants' service providers (e.g., case managers) at the supportive housing agency. Participants who during the course of the project are in need of detoxification and are at acute risk of suicide or homicide will be referred for treatment and discontinued from the study. Moreover, participants that develop contraindications to participating in a weight loss program, such as receiving active cancer treatment (radiation/chemotherapy), develop liver failure, have a cardiovascular event (e.g., unstable angina, myocardial infarction) and become pregnant or are planning a pregnancy during the study period will be discontinued from the study.

4. Study Drugs or Devices: Not applicable.

5. Study Instruments

Structured Interviews: Baseline and 6, 12, and 18-month Follow-Up

The structured interview includes the collection of basic anthropometric measures and a simple physical activity measure by trained research staff:

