"Thank you for your interest in our study. The purpose of this project is to evaluate a free group-based healthy lifestyle program to help [Agency] clients who are overweight or obese reduce and manage their weight. The goal of this program is help participants improve their eating habits and increase their engagement in physical activities. The study is being conducted through a partnership between [Agency] and the Columbia University School of Social Work. If you are eligible and you choose to participate, you will be randomly assigned to either 1) continue receiving your usual services or 2) to continue receiving your usual services plus participate in a 12-months healthy

lifestyle program that will be held at [site]. Random assignment is like a lottery and means that you have a 50/50 chance of being assigned to either group. If you are not randomly assigned to receive the healthy lifestyle program, you will continue receiving your usual services, but you will not participate in the healthy lifestyle program. If you are randomly assigned to receive the healthy lifestyle program, you will continue receiving your usual services and you will also be asked to attend the healthy lifestyle groups every week for 12 consecutive weeks. After you attend the program for 12 weeks, you will be asked to attend follow-up groups once a month for 9 months. Each group will last approximately 90 minutes and will be facilitated by a trained peer specialist.

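### The recruitment script leaves out the twice-monthly phase of Peer GLB, so candidates are told at first contact about three fewer sessions in months 4-6 than the protocol plans

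*Combined protocol and SAP*

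**What the plan says.** Section 2 (Study Design and Statistical Procedures) sets out the 12-month intervention as "weekly core group sessions (3 months.), bimonthly (twice a month) transitional group sessions (3 months.), and monthly maintenance sessions (6 months". The intervention description in Section 3 repeats this: "GLB consists of weekly core group sessions (3 months), bi-monthly (twice a month) transitional group sessions (3 months), and monthly maintenance sessions (6 months".

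Section 3 also relies on the middle phase as a time point: "This semi-structured qualitative interview will be conducted after the transition phase of an intervention group has been completed". The interview is tied to the same phase in Section 5 (Study Instruments), in the compensation text of Section 7 and in Section 8 (Informed Consent Process).

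Section 7 prescribes a script for explaining the study to interested clients and inviting them to screening. It describes weekly groups for 12 consecutive weeks and continues: "After you attend the program for 12 weeks, you will be asked to attend follow-up groups once a month for 9 months". It gives the length of each group as about 90 minutes. It mentions no twice-monthly phase.

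**The concern.** Two current parts of the same document give different session schedules for the intervention arm, and nothing reconciles them. One is the definition of the intervention. The other is fixed wording that staff use with candidates.

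Two things are at stake. The first is the accuracy of what candidates hear about the time commitment, which bears on their interest because Section 7 pays for assessments and not for attending sessions. The second is a single clear statement of the planned exposure. The protocol gives no total session count, so anyone who needs one must derive it from a schedule, and there are two.

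**Working it through.** There is no stated total to reproduce. The check is session frequency multiplied by duration, summed over phases.

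**Inputs**
- Section 2, core phase: weekly for 3 months, taken as 12 sessions (13 if three months is counted as 13 weeks).
- Section 2, transitional phase: "bimonthly (twice a month) transitional group sessions (3 months".
- Section 2, maintenance phase: "monthly maintenance sessions (6 months".
- Section 7 script: 12 weekly groups, then one group a month for 9 months, each of about 90 minutes.

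**Sessions by period**

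| Period | Sections 2 and 3 | Section 7 script |
|---|---|---|
| Months 1-3 | 12 | 12 |
| Months 4-6 | 2 × 3 = 6 | 1 × 3 = 3 |
| Months 7-12 | 1 × 6 = 6 | 1 × 6 = 6 |
| Total | 12 + 6 + 6 = 24 | 12 + 9 = 21 |

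**Differences**
- Total duration: 3 + 3 + 6 = 12 months against 3 + 9 = 12 months. These agree.
- Months 4-6: 6 − 3 = 3 sessions, which is half of the 6.
- Overall: 24 − 21 = 3 sessions, and 3/24 = 12.5%.
- Time in groups: 24 × 1.5 = 36.0 hours against 21 × 1.5 = 31.5 hours, a difference of 4.5 hours.

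**Sensitivity to the count of weeks.** With 13 core sessions, the protocol total is 13 + 6 + 6 = 25, and the gap is 25 − 21 = 4 sessions (4/25 = 16%). The extra session comes from how the core phase is counted. The gap of 3 in months 4-6 is unchanged.

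**Could the texts be read as agreeing?** The ambiguity of bimonthly does not help, because both Section 2 and Section 3 define it as twice a month. Rounding does not help either, because the periods before and after months 4-6 match. Nothing is blacked out in the sentences concerned, and neither is superseded text. On the script's schedule there is no transition phase, so the time point for the qualitative interview (55 participants expected) would not exist.

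**The case against.** The strongest reply is that this is one inaccurate description in a recruitment script, with little shown to follow from it. Much of that stands. Several larger conclusions that a reader might draw are not supported.

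- **That participants join the trial on the wrong schedule.** The script is used before screening. Agreement comes later, at written consent, where Section 8 says study procedures are discussed and understanding is tested. The consent form is not among the documents, so it can be neither relied on nor faulted.
- **That the script causes missed sessions that are then misread as poor engagement.** Section 3 gives participants a program calendar, and Section 7 has staff telephone them one or two days before each session. An effect on attendance is conceivable but not shown.
- **That attendance or completion figures are distorted.** Section 1 mentions attendance logs and completion records. No section defines an attendance rate, an adherence threshold, a per-protocol population or a dose analysis. A score such as 21/24 = 88% would need a denominator that the plan does not set. The only attendance cut-off is two sessions, for the qualitative interview, and either schedule meets it easily.
- **That a different programme is being tested, or that the two texts cannot both be followed.** The script informs candidates. It does not instruct facilitators, who have a session-by-session manual. Duration, the weekly phase, months 7-12 and peer facilitation are not in dispute.

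It is also fair to say that the script is the only place that lacks the transition phase. That makes it the outlier, but it does not by itself settle which schedule was intended. None of these replies makes the two schedules agree.

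**Conclusion.** The inconsistency is real and confined to months 4-6: 6 sessions in Sections 2 and 3, 3 in the Section 7 script. Candidates are told at first contact of a commitment lighter by about three 90-minute sessions than the protocol plans. The totals of 24 and 21 are derived, and 24 assumes 12 weekly core sessions (25 on a 13-week count). The finding for months 4-6 does not depend on that assumption.

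The point concerns what candidates are told and the consistency of the stated schedule. It does not touch sample size, error rate or power, and the documents show no effect on the primary comparison at 12 and 18 months. It deserves correction because the wording is prescribed, faces participants and is easily put right.

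**What to change.** Reconcile Section 2, the intervention description in Section 3 and the script in Section 7 to one schedule, and state the total number of sessions once. Carry that schedule into the script and all other participant-facing text, and check the consent form against it. Confirm that the qualitative interview is still tied to a phase that exists in the agreed schedule. If the script has already been used, record which schedule each cohort was told and which it received. The documents do not settle which schedule is intended, so that is for the investigators to decide.

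The cost is a wording amendment with IRB notification, plus a short record for any cohorts already recruited. No study procedure is added.

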Potential Risks and Procedures to Minimize Risks Associated with Participating in the Peer GLB Intervention: There is a small risk of injury while engaging in physical activity, but this will be minimized by recommending that participants in the Peer GLB intervention engage only in moderate physical activity (e.g., brisk walking 30 minutes a day), as opposed to engaging in more vigorous physical activity (e.g., running). There is a small risk of having inadequate nutrition or experiencing excessive, rapid weight loss due to changes in diets. For participants taking antidiabetic medications, changes in diet and physical activity may increase the risk of having low blood sugar levels, especially at the beginning when participants start making these changes. For

participants taking medication that lowers blood pressure, weight loss interventions have the potential to increase the risk of having blood pressure that is too low.

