We will take several steps to minimize all of these risks. All participants randomly assigned to the Peer GLB intervention will be referred to a medical provider to determine whether it is safe for them to participate in the intervention prior to beginning Peer GLB. Only participants who obtain this medical clearance will be able to participate in the Peer GLB intervention. We will further minimize these risks through group sessions and individual counseling that will teach participants about: 1) the importance of properly engaging in moderate physical activity, warm-up and cool-down exercises, proper stretching and exercise techniques; 2) the importance of eating a variety of foods from all food groups, taking in enough calories, and losing weight safely and slowly as recommended and emphasized in the program; 3) and the importance of understanding and monitoring potential symptoms of low blood sugar and low blood pressure. Additionally, study staff and peer specialists delivering the intervention will also periodically (e.g., weekly basis) review participants' food logs, weight logs, self-monitoring tools and provide feedback to Peer GLB participants on whether they are taking in enough nutrients. If there is any question about the cause of an injury or the need for treatment, or if a participant experiences sudden, dramatic weight loss, or signs of low blood sugar or low blood pressure, we will refer them to their physician and stop the intervention as recommended by their physician. The project also has primary care physician, [name], readily available to provide consultation to study staff regarding any potential medical issues.

12. Data and Safety Monitoring

Describe how data and safety will be monitored locally to identify unanticipated problems (i.e., events, outcomes, or occurrences that are unexpected, at least possibly related to the research, and suggest an increase in risk of harm to subjects or others). [name] (PI) and [name] (Project Director) will be responsible for data and safety monitoring. The following steps will be used for data and safety monitoring:

1. At Bi-monthly meetings (twice a month), the PI and Project Director will review rates of enrollment and study retention, any problems with participant safety, and the status of data collection. Protocol violations will be discussed and, if appropriate, the IRBs will be consulted and corrective actions devised.

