2. Although the risks to participants from this protocol are likely to be low (given medically unstable participants are excluded), these risks will be continuously monitored and appropriate measures implemented in cases of unforeseen adverse events, including the removal of participants from the study protocol. For example, if participants became suicidal during the protocol, they would be removed from the study and given appropriate clinical care at the study site.
3. Every 2 months during the intervention phases of the study, the PI and Project Director will review the number of participants enrolled, the number who discontinued participation (and reasons why), the number who did and did not complete study procedures (and reasons why), any adverse events, procedures for assuring participant privacy and confidentiality, and the quality and integrity of the data collected. Corrective action will be taken if needed.

4. IRB protocols and informed consent documents will be reviewed annually by the CU IRB and respective IRBs (e.g., supportive housing agency IRB). Reports of enrollment and retention and reporting of adverse events are required with these renewals. Research Meetings for Data Safety and Monitoring: Throughout the project, frequent research staff meetings will be held with all study personnel to coordinate the study and to assess the progress and status of participants. The PI and Project Director will supervise the day-to-day operations of the study staff. Ad hoc meetings will be performed at Columbia University School of Social Work Offices or study sites with Co-investigators, in order to discuss and resolve any participant-specific issues. These meetings will be attended by the PI, Project Director and study staff. In addition, monthly regular project steering committee with the PI, study staff, representatives from study sites and Co-investigators will be performed to discuss general updates and performance of the project.

Adverse Events: In consultation with the DSMB and pursuant to Human Subjects Regulations and CU IRB protocol, the PI will adhere to the following protocol for adverse events.

- 1) Adverse events may be initially identified by RAs, the Project Director, PI, or other project staff, including staff reviewing audio recordings of Peer GLB sessions, or they may be reported by participants or their providers at the supportive housing agency.

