- 2) Within 24 hours of an adverse event being identified, an Adverse Event Report form will be completed by the study staff member or supportive housing provider who identified the event. The report form will include date, description of the event, duration, severity, measures taken to ameliorate the adverse event, and disposition related information (e.g., time spent providing referrals and type of referral (e.g., mental health treatment, ER visit, etc.). The report form will be reviewed and signed by the immediate supervisor who will be responsible for ensuring that appropriate actions have been taken.
- 3) Once the PI becomes aware of an adverse event, he will, in consultation with the study physicians as necessary, assess the event to determine whether the adverse event was an unanticipated problem by evaluating 1) was it unexpected, and if so, 2) was it possibly related to study participation, and if so, 3) does it qualify as a serious adverse event or suggest that the research places subjects or others at greater risk of harm than previously recognized. In making this determination, the PI will consult with housing provider staff and the physician co-investigators on the study, as well as review any documentation or other sources to clarify the nature of the event and outcomes. The PI will report any events that meet the three criteria to the IRB as unanticipated problems within 1 week of the PI becoming aware of the event. The PI will consult with the investigative team, DSMB, and supportive housing provider to determine whether protocol changes are needed. The PI will maintain a log of all adverse events and present a summary report for the DSMB to review.
- 4) The investigative team and the DSMB will review all adverse event data every six months to determine if systematic trends exist among adverse event data to warrant changes to study protocols and procedures. Any proposed changes will be reviewed with staff at the study sites, and, if needed, external consultant (e. g., other senior investigators conducting federally-funded research on the physical health of people with SMI).

Approval for changes in study protocol or materials will then be obtained from the Columbia University IRB and other study site's IRB. After approval, the NIMH program official will be

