What is Monitored: The DSMB will evaluate the progress of the trial, recruitment rates, retention rates, adverse events, unanticipated problems, and other factors affecting safety or outcomes. The DSMB will review rates of adverse events in the study (in an unblinded manner if they wish) to evaluate any changes in participant risk. The PI, Project Director, and study statistician ([name]) will be available to the DSMB to provide summary data on recruitment, data quality, adverse events, and will provide requested data analyses. The DSMB also will review major proposed modifications to the study prior to their implementation.

Confidentiality: The DSMB will not have access to personally identifiable information of participants. DSMB members agree not to disclose the results of the data except as agreed by the PI. The report to the DSMB includes actual vs. projected recruitment rates (number screened, consents, randomized, etc.), summary of serious adverse events, and any modifications to the protocol.

Communication Plan: At the end of each DSMB meeting, the chair will provide the study leadership with written information concerning findings for the trial as a whole and any relevant recommendations related to continuing, changing, or terminating the trial. The chair will prepare a summary of the meeting along with any recommendations for changes to the protocol based on the meeting. The draft report will be reviewed and edited by all Board members prior to issuing the final report. This report will not include confidential information. The report should indicate whether the study should continue as originally designed, whether the study should be modified to protect patient safety or whether the study should be terminated. The PI will send the report to the Columbia University IRB, other study site's IRBs, and to the sponsoring NIH Institute.

13. Potential Benefits

The potential benefits to participants are direct (improved health and wellness) and indirect (helping to refine the appropriateness and promote the use of a promising group-based healthy lifestyle intervention). The study will test the effectiveness of Peer GLB to improve the physical health of culturally diverse consumers with serious mental illness who are overweight or obese receiving services at supportive housing agencies.

14. Alternatives

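### Adverse events are looked for more closely in Peer GLB than in usual care, no listed instrument asks both arms about the intervention's main physical risks, and the listed report form fields do not record how an event was found

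*Combined protocol and SAP*

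**What the plan says.** Section 12 (Adverse Events) lists who may first identify an event: research assistants, the Project Director, the principal investigator, or "other project staff, including staff reviewing audio recordings of Peer GLB sessions, or they may be reported by participants or their providers". The report form is to be "completed by the study staff member or supportive housing provider who identified the event" within 24 hours. On its content: "The report form will include date, description of the event, duration, severity, measures taken to ameliorate the adverse event", followed by disposition and referral details. How the event came to light is not among the listed fields.

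Several routes exist only in Peer GLB. All its group sessions are recorded and the recordings reviewed (section 3). It has facilitated sessions over 12 months (section 2), with reminder calls before each (section 7). Section 11 adds that "study staff and peer specialists delivering the intervention will also periodically (e.g., weekly basis) review" participants' food logs, weight logs and self-monitoring tools.

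Other routes serve both arms: the 6, 12 and 18 month interviews, participants' own reports, and agency providers. The interviews include BASIS-24, with a fixed action rule for thoughts of suicide or self-harm (section 3), weight, blood pressure and service use (section 5).

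Section 11 names the intervention's risks. On exercise: "There is a small risk of injury while engaging in physical activity". For people on antidiabetic drugs, "changes in diet and physical activity may increase the risk of having low blood sugar levels". Blood pressure that is too low is named for those on pressure-lowering drugs.

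On use of the data, the DSMB is to "review rates of adverse events in the study (in an unblinded manner if they wish) to evaluate any changes in participant risk", and its chair reports "recommendations related to continuing, changing, or terminating the trial" (section 12, What is Monitored and Communication Plan).

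**The concern.** A count of logged events depends on how often events happen and on how likely each is to be noticed. Here the second factor differs by arm by design. The extra routes can only add logged events in Peer GLB. They are densest in the first three months, when sessions are weekly; section 11 also expects low blood sugar to be most likely early on. Real risk and surveillance would therefore rise together.

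At stake is how a between-arm difference in adverse events is read. If the board looks at rates by arm and sees more in Peer GLB, the log as described would not reliably show how much came from the intervention and how much from closer watching. Equally, a real excess could be dismissed as an artefact of observation.

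**Working it through.** The plan gives no figure on adverse event detection, so there is nothing to reproduce. The check has four steps.

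**1. Scheduled study contacts after baseline, at full attendance.** Section 2 gives weekly sessions for 3 months (12 to 13), twice-monthly sessions for 3 months (6) and monthly sessions for 6 months (6), which makes 24 to 25. The recruitment script in section 7 gives 12 + 9 = 21. Adding the 3 follow-up interviews:

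- Peer GLB: 21 + 3 = 24 up to 25 + 3 = 28
- Usual care: 3

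Reminder calls are not counted. This shows unequal opportunity and is not a detection ratio. Agency contact comes on top in both arms, and Peer GLB participants without medical clearance attend no sessions.

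**2. Stated risks set against instruments collected in both arms.**

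| Risk in the plan | Listed question or measurement in both arms |
|---|---|
| Suicidality, self-harm | BASIS-24 at every assessment |
| Excessive weight loss | Weight at every assessment |
| Low blood pressure | Seated reading at the visit; no symptom question |
| Injury | None listed |
| Low blood sugar | None listed |

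Service use may pick up events that led to care, but it is not a question about these risks.

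**3. Illustration of size.** Every rate here is an assumption: equal true 18-month risk *t* of 0.15 to 0.35; shared routes find a fraction *d0* of affected participants; Peer GLB-only routes find a fraction *d1* (0.20 to 0.50) of the rest, averaged over everyone randomized. The 150 per arm is from section 1.

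- Logged risk, usual care: t × d0
- Logged risk, Peer GLB: t × (d0 + (1 − d0) × d1)
- Ratio: 1 + (1 − d0) × d1 / d0
- Extra Peer GLB participants logged: 150 × t × (1 − d0) × d1

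| d0 | Ratio, d1 = 0.20 to 0.50 | Extra of 150, over t and d1 |
|---|---|---|
| 0.30 | 1.47 to 2.17 | 3.2 to 18.4 |
| 0.45 | 1.24 to 1.61 | 2.5 to 14.4 |
| 0.60 | 1.13 to 1.33 | 1.8 to 10.5 |
| 0.80 | 1.05 to 1.13 | 0.9 to 5.3 |
| 0.90 | 1.02 to 1.06 | 0.5 to 2.6 |

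The largest ratio is 1 + 0.70 × 0.50 / 0.30 = 2.17; the smallest is 1 + 0.10 × 0.20 / 0.90 = 1.02. The documents cannot say which row applies.

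**4. Precision of a comparison on common assessments.** Assume *m* = 120 to 150 assessed per arm and *p* = 5 to 20% reporting an event in each. The 95% CI half-width for the risk difference is 1.96 × √(2p(1 − p)/m). With p = 0.05 and m = 150 it is 4.9 percentage points; with p = 0.20 and m = 120 it is 10.1. The comparison would be descriptive.

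**The case against.** The strongest reply is that the plan makes no between-arm claim about adverse events. They are not listed as an outcome, no test is stated, and the DSMB sees rates by arm only if it chooses. The report to the DSMB is described as summarising serious events, which are probably less sensitive to how closely people are watched. Whether an event is an unanticipated problem is judged individually, with physicians and housing staff. Watching the exposed arm more closely is also sound safety practice. All of this stands and limits the importance. It does not remove the asymmetry: section 12 also has the principal investigator present a summary of the log of all adverse events to the DSMB, and all adverse event data are reviewed for trends that might justify protocol changes.

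The interview and the report form are not reproduced, and part of section 12 is absent from the available text. The point therefore rests on listed content; either form may already hold what is asked for.

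Some stronger readings are tempting but unsupported:

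- A reader might infer that nothing is asked uniformly. BASIS-24, blood pressure, weight and service use are.
- A reader might infer that usual care clients have no contact with peer specialists. These are agency employees, and ordinary contact is not excluded. Only contact at sessions is specific to Peer GLB.
- A reader might infer that the 12-month look-back of the service-use item adds to the imbalance. Any such window applies equally to both arms.
- A reader might infer that the route of detection is lost entirely. The completer, dates, attendance logs and retained recordings allow partial reconstruction. It is not dependable, because section 3 gives both assessments and recording review to trained research assistants.

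**Conclusion.** The point holds in limited form. Detection opportunity is unequal by arm, the physical risks named in section 11 are not covered by a common question in the listed instruments, and the listed form fields do not record the route. An excess of logged events in Peer GLB could therefore arise without any excess of harm.

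The size is unknown. The ratios of 1.02 to 2.17 rest wholly on assumed risks and detection fractions; if shared routes already find 80 to 90% of events, the ratio is at most about 1.13. A reader might take the 24 to 28 against 3 contacts as the size of the bias, or expect the board to be misled; the documents support neither. Serious events are probably less affected, and the efficacy analyses are not affected. Importance is minor to moderate, and the change is worth making because it costs little.

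**What to change.** Add to section 12:

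1. At 6, 12 and 18 months the research assistant asks every participant in both arms the same short list: injury, fainting or dizziness, low blood sugar, and emergency visit or hospital stay since the last assessment.
2. The Adverse Event Report form records how the event was first identified: scheduled assessment; Peer GLB session, log or recording; agency provider; other.
3. Whenever adverse events are summarised by arm, all events are shown and, beside them, participants with an event reported at the common scheduled assessments, whether or not already logged: number and percent of those assessed, risk difference and 95% CI. Deaths and events leading to discontinuation are shown by arm on a separate line.

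The separate line is needed because section 3 discontinues participants after certain events, so they may never reach a later interview. It should be read with care: section 3 has discontinuation ascertained by the group facilitator with agency providers, and usual care has no facilitator.

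All events still go to the DSMB. No hypothesis test is added, and the referral, stopping and reporting rules are unchanged.

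The cost is a few minutes in an interview of about 60 minutes, one form field and one table, with no new visits or staff. Six-month recall will miss minor events in both arms. Some difference in reporting will remain, because Peer GLB teaches participants to recognise symptoms of low blood sugar and low blood pressure.
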